8.2.9. Absolute and Percentage Changes in Serum β -D-Glucan from Baseline

Serum β -D-glucan is assessed at screening, Day 1, Day 3, Day 5, Day 7, Day 10, Day 14, then every 14 days during treatment, at EoT and at Follow-up.

Absolute change from baseline in serum β -D-glucan will be summarized, by treatment, for the ITT Population at Week 1 (Day 7), Week 2 (Day 14), Week 4 (Day 28) and Week 6 (Day 42).

In addition, percentage change from baseline will also be summarized.

8.2.10. Percentage of Subjects with Target Changes in Serum β -D-Glucan from Baseline

The percentage of subjects with the following target changes in serum β -D-glucan from baseline will be presented at Weeks 1, 2, 4 and 6 for the ITT Population:

- Fifty percent reduction or greater
- Twenty-five percent reduction or greater
- Any percent reduction
- Negative serum β -D-glucan

The difference in rates between treatments will be presented along with a 95% CI calculated using the method of Clopper-Pearson.

8.2.11. Percentage of Subjects that Convert from Positive Plasma *Aspergillus* PCR at Baseline to Negative

The percentage of subjects that convert from positive plasma *Aspergillus* PCR at baseline to negative will be presented at Weeks 1, 2, 4 and 6 for the ITT Population.

The difference in rates between treatments will be presented along with a 95% CI calculated using the method of Clopper-Pearson.

8.2.12. Absolute Change in Karnofsky Score from Baseline to Days 42 and 84

Karnofsky Performance Status is assessed at screening, Day 1, Day 14, Day 28, Day 42, Day 56, Day 70 and Day 84.

Karnofsky Performance Status will be summarized as a categorical variable at each visit.

In addition, taking Karnofsky Performance Status as a continuous variable, absolute change from baseline in Karnofsky score will be summarized, by treatment, for the ITT Population at Day 42 and Day 84.

8.2.13. Time to Achieve a 10-Point Improvement in Karnofsky Score from Baseline

Time to achieve a 10-point improvement in Karnofsky score from baseline will be expressed in days and calculated using the formula:

$$\text{Time to Achieve} = \text{Date of Achievement/Censoring} - \text{Date of Randomization.}$$

Subjects not achieving the 10-point improvement by Day 84 will be censored at their last Karnofsky assessment date, date of withdraw, date of death or at Day 84 whichever comes first.

The number and percentage of subjects with events and censored will be summarized.

The Kaplan-Meier method will be used to estimate the distribution of time to achieve target for each treatment group. The 25th percentile, median and 75th percentile and their 95% CIs will be presented.

8.2.14. Percentage of Subjects with a Recurrence of the Baseline Fungal Infection within 42 Days (Week 6) after EoT

Assessment of recurrence of the baseline fungal infection will take place at the follow-up visit, 6 weeks after EoT.

The percentage of subjects with a recurrence will be summarized, by treatment, for the ITT Population. The denominator for the percentage will be the number of subjects without the baseline fungal infection at EoT.

8.2.15. Relationship Between Serum GMI Decrease and ACM at Days 42 and 84 for subset of patients with positive serum galactomannan at baseline

At Day 42, subjects will be categorized as dead or alive. For each of these two groups of subjects, a boxplot will be presented showing their last available GMI decrease, up to and including Day 42. Should a subject have no post baseline GMI data then they will not be included in the plot. The plot will be based on the ITT Population.

The above plot will be repeated for Day 84.

8.2.16. Relationship between serum GMI decrease and global response at D42 and EOT for subset of patients with positive serum GM at baseline**8.2.17. Relationship between serum GMI decrease and clinical response at D42 and EOT for subset of patients with positive serum GM at baseline****8.2.18. Relationship between serum GMI decrease and radiological response at D42 and EOT for subset of patients with positive serum GM at baseline****8.2.19. Number of subjects with complete response and alive at Day 42 and at Day 84****8.2.20. Days of Hospital Stay and Days of ICU Stay**

For each subject the number of days of hospital stay and the number of days of ICU stay will be calculated.

These both will be summarized, by treatment, for the ITT Population.

8.2.21. Percentage of Subjects Who are Able to Receive On-Schedule Administration of the Planned Therapies for their Underlying Condition

The number and percentage of subjects who received on-schedule administration of the planned therapies for their underlying condition will be summarized.

In addition, the number of subjects with a delay to their planned therapy, and the duration of the delay will also be summarized.

Summaries will be for the ITT Population.

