15.22 Recurrence

Recurrence (after EoT) will be assessed by measuring recurrence of the baseline fungal infection within 42 days after EoT (6-Week FU). The DRC will be responsible for determining recurrence.

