4.2. Secondary Endpoints

- Global Response as measured by:
 - Percentage of subjects with Complete Response or Partial Response at EoT (key secondary endpoint), Day 42 and Day 84, as determined by the DRC
 - Percentage of subjects with Complete Response or Partial Response at EoT, Day 42 and Day 84, as determined by the Principal Investigator
- Overall survival, defined as the time from randomization to time of death up to Day 84
- Percentage of subjects who died (any cause) at Days 42 and 84
- Absolute reduction and percent change in serum GMI from Baseline to Weeks 1, 2, 4 and 6
- Percentage of subjects with the following changes in serum GMI from Baseline:
 - Fifty percent reduction or greater at Weeks 1, 2, 4 and 6
 - Twenty-five percent reduction or greater at Weeks 1, 2, 4 and 6
 - Any percent reduction at Weeks 1, 2, 4 and 6
 - Reduction equal to or greater than 0.25 at Weeks 1, 2, 4 and 6
 - Reduction to <0.5 at Weeks 1, 2, 4 and 6
- Time to achieve the following changes in serum GMI from Baseline:
 - Fifty percent reduction
 - Twenty-five percent reduction
 - Any percent reduction
 - Reduction equal to or greater than 0.25
 - Reduction to <0.5 in 2 consecutive samples
- Percentage of subjects with:
 - Clinical Response at EoT, Day 42 and Day 84, as determined by the DRC
 - Mycological Response at EoT, Day 42 and Day 84, as determined by the DRC
 - Radiological Response at EoT, Day 42 and Day 84, as determined by the DRC

- Percentage of subjects with:
 - Clinical Response at EoT, Day 42 and Day 84, as determined by the Principal Investigator
 - Mycological Response at EoT, Day 42 and Day 84, as determined by the Principal Investigator
 - Radiological Response at EoT, Day 42 and Day 84, as determined by the Principal Investigator
- Ibrexafungerp and voriconazole plasma concentrations population PK analysis.

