 - No attributable signs and symptoms present at Baseline and no symptoms attributable to invasive fungal disease developed post Baseline

Mycological response

- Success:
 - Eradication
 - Presumed eradication
- Failure:
 - Persistence
 - Presumed persistence
- Not applicable:
 - No mycological evidence available at Baseline

Radiological response

Day 42:

- Success (improvement of at least 25% from Baseline)
- Failure
- No post Baseline radiology available for patient with baseline evidence of radiological disease
- Radiology not applicable at Baseline

Day 84:

- Success (improvement of at least 50% from Baseline)
- Failure
- No post Baseline radiology available for patient with baseline evidence of radiological disease
- Radiology not applicable at Baseline

EoT:

- Success (improvement of at least 25% from Baseline if EoT occurs prior to Day 42; if EoT occurs after Day 42, at least 50% improvement from Baseline)
- Failure
- No post Baseline radiology available for patient with baseline evidence of radiological disease
- Radiology not applicable at Baseline

Recurrence, at 6-week FU visit

Recurrence is defined as a diagnosis of probable or proven IPA (based on EORTC) after EoT in patients who have previously achieved complete response. Re-emergence of the *Aspergillus* infection is required to be with the same species (if *Aspergillus* isolates are available for both the baseline and the recurrent episode) and involving the same site that was initially identified at Screening.

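### Recurrence within 42 days of EoT is assessed only at the 6-week follow-up visit, over a denominator fixed at EoT with no rule for unassessed subjects, so the rate is understated

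*SAP*

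**What the plan says.** **The event is defined over a window.** Protocol 15.22 measures "recurrence of the baseline fungal infection within 42 days after EoT", and the endpoint in SAP 4.3 and the heading of SAP 8.2.14 use the same 42 days. SAP 14.1 defines the event by diagnosis, with no visit attached: "Recurrence is defined as a diagnosis of probable or proven IPA (based on EORTC) after EoT in patients who have previously achieved complete response". Protocol 15.22 assigns the decision: "The DRC will be responsible for determining recurrence".

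**The assessment is placed at one visit.** SAP 8.2.14: "Assessment of recurrence of the baseline fungal infection will take place at the follow-up visit, 6 weeks after EoT". SAP 14.1 heads its definition "Recurrence, at 6-week FU visit". The schedules (SAP Table 1, Protocol Table 4) mark the assessment of recurrence in the 6-week follow-up column only. SAP 6.1 summarizes data at nominal time points and only lists repeat and unscheduled assessments.

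**The denominator is set earlier.** SAP 8.2.14: "The denominator for the percentage will be the number of subjects without the baseline fungal infection at EoT". SAP 13.2.5.2 would otherwise base percentages on subjects with an observation, but that default gives way where a section states its own rule, as 8.2.14 does.

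**Nothing covers loss after EoT.** SAP 6.3 and Protocol 19.4 deal with a missing EoT assessment. SAP 8.1 deals with missing response data at EoT, Day 42 and Day 84. Neither document says how a death or a missed follow-up visit counts for recurrence.

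**The concern.** Numerator and denominator follow different rules. A subject enters the denominator by being free of infection at EoT, but as the SAP is worded can enter the numerator only through an assessment six weeks later. Anyone who does not reach that assessment contributes one to the denominator and nothing to the numerator.

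For Global Response, keeping subjects with missing data in the denominator is conservative, because the event counted is a favourable one. Recurrence is an unfavourable event, so the same device flatters the result. If the arms differ in missed visits, or in deaths with an unrecorded recurrence, the arm that loses more subjects shows the lower recurrence rate for that reason alone.

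**Working it through.** The documents state no recurrence rate, no follow-up loss and no sample-size calculation, so there is no figure of the plan's to reproduce. The rates below are assumptions, used to show direction and scale.

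**Notation.** D = subjects free of the baseline infection at EoT; r = recurrences recorded; m = subjects in D not assessed at follow-up; p = true recurrence risk; q = share of D not assessed.

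**1. Expected understatement when subjects go unassessed at random.** Expected reported rate = p × (1 − q). With p = 20% assumed:

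- q = 10%: 20% × 0.9 = 18%
- q = 20%: 20% × 0.8 = 16%
- q = 30%: 20% × 0.7 = 14%

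Two arms with the same 20% risk, one losing 10% and the other 30%, would show 18% against 14%: a 4-point difference in favour of the arm with more losses. If subjects with a recurrence are more likely to be missed, the shortfall is larger.

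**2. A small-sample example.** SAP 3.4 gives about 11 subjects per group, and D can be no larger. Assume D = 8, r = 1, m = 2, with exact 95% intervals:

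- EoT denominator, as planned: r/D = 1/8 = 12.5% (0.3% to 52.7%)
- Assessed subjects only: r/(D − m) = 1/6 = 16.7% (0.4% to 64.1%)
- Every unassessed subject counted as an event: (r + m)/D = 3/8 = 37.5% (8.5% to 75.5%)

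The first and third are the lowest and highest rates that the unknown outcomes allow. One subject moves the rate by 1/11 = 9.1 points at D = 11 and by 1/6 = 16.7 points at D = 6.

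**3. Deaths and missed visits are different losses.** A subject who dies without recurrence did not recur. Leaving that subject in D gives the ordinary cumulative incidence of recurrence with death as a competing event. The dilution is a fault only for unassessed survivors and for recurrences that were never recorded. If, in the example, one of the two lost subjects died without recurrence and the other is alive but unassessed, the rate excluding only the latter is 1/7 = 14.3%, and recurrence-or-death is (1 + 1)/8 = 25.0%.

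**4. Whether the survival endpoints fill the gap.** SAP 4.2 has "Overall survival, defined as the time from randomization to time of death up to Day 84", and SAP 8.2.3 counts deaths by Day 42 and Day 84. Protocol 15.25 allows up to 91 days of treatment. Follow-up day = EoT day + 42:

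- EoT Day 42: follow-up Day 84; no part of the window lies after Day 84
- EoT Day 56: follow-up Day 98; 98 − 84 = 14 days lie after it
- EoT Day 84: follow-up Day 126; all 42 days lie after it
- EoT Day 91: follow-up Day 133; all 42 days lie after it

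The survival endpoints therefore cover the whole window only when treatment ends by Day 42, the recommended minimum of six weeks.

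**The case against.** A fair defence has four parts.

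- **No stated scoring rule.** A reader might infer that the plan scores dead or absent subjects as recurrence-free. It does not. No section assigns them that outcome, and SAP 13.2.5.2 adds an unknown or missing category where information is lacking, so they could appear in a row of their own. This stands, but a separate row does not take them out of the denominator, and the percentage stays diluted.
- **Fatal recurrences are not necessarily lost.** A reader might infer that any recurrence that kills before the visit disappears. The definition turns on a diagnosis after EoT and the DRC decides, so one diagnosed before death qualifies on its face. The schedule allows imaging and mycology at unscheduled visits, and the protocol collects mycology results up to follow-up and antifungal use after EoT. The exclusion of unscheduled assessments in SAP 6.1 may not have been meant to bind a DRC decision, and the DRC charter is not among the documents. This stands too. The loss is certain only for a recurrence never diagnosed; for one found at an unscheduled visit it depends on following SAP 8.2.14 and 6.1 to the letter. The SAP should not leave that open.
- **The deaths are reported elsewhere.** Deaths belong to the primary safety endpoint, adverse events are collected to the end of the study, and SAP 10.3 tabulates those leading to death by arm. This stands, though those tables do not link a death to recurrence.
- **Low stakes.** The endpoint is exploratory and descriptive, with about 11 subjects per arm and no interval or test planned. This stands and limits the weight of the point.

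**Conclusion.** The concern holds in a limited form. The visit-based wording of SAP 8.2.14 and 14.1 does not match the 42-day window of the endpoint. With the denominator fixed at EoT and no provision for subjects not assessed, the rate is understated, more so in the arm with more losses. That follows from the stated rule. Its size depends on rates the documents do not give: under the assumed 20% risk with losses at random, 2 to 6 percentage points for 10% to 30% unassessed.

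It would be tempting to size the problem from the 6-week mortality in the randomized combination trial described in Protocol 8.1. The documents do not support that. Those deaths are counted from the start of treatment for acute disease, whereas recurrence concerns subjects who have already responded and finished treatment; and they are deaths from any cause, not missed recurrences.

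This is a minor correction, worth making because at these numbers one subject shifts the rate noticeably.

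**What to change.** Amend SAP 8.2.14, with a matching change to the heading of the recurrence definition in SAP 14.1:

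1. Count every recurrence determined by the DRC from EoT to 42 days after EoT, whether or not the follow-up visit took place, including those found at unscheduled visits or before death. State that SAP 6.1 does not exclude them.
2. Report by arm, as separate rows, subjects who died before assessment without a documented recurrence and subjects who were alive but not assessed. Give the rate with unassessed survivors excluded next to the rate on the EoT denominator.
3. Optionally, show recurrence-or-death within 42 days of EoT as a supportive sensitivity rate, with a note that it includes deaths from other causes.

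The cost is a few sentences and a few table rows. No new visit or procedure is needed, since deaths in the window are already collected through adverse event reporting. The counting rule should be settled before the database lock and unblinding described in SAP 3.7.

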This study will evaluate the safety of SCY-078 when coadministered with voriconazole to the intended population. This Phase 2 study also aims to investigate the effect of the coadministration of SCY-078 with voriconazole on multiple outcome endpoints including ACM and global response (typical endpoints for this indication) but also investigates other biological markers of therapeutic response such as serum galactomannan index. The information from this study is expected to guide the selection of clinically relevant endpoints to evaluate subsequently in a larger Phase 3 study.

Rationale for proposed doses Voriconazole

The subjects in the study will receive either intravenous or oral formulation of voriconazole, as indicated and per investigator's discretion. Typical regimen for IPA includes start of therapy with the IV formulation of voriconazole with subsequent step-down to oral formulation. The doses of voriconazole will be as recommended in the label. The drug-drug interaction simulation PBPK-based model does not indicate any need for a modification to the approved dose of voriconazole when coadministered with SCY-078. Therapeutic drug monitoring will follow label recommendation and also local practices. Modifications to voriconazole dose will be allowed aiming to maintain recommended serum concentration target ranges above 1.5 mg/L and to avoid potential toxicities associated with high exposure (i.e., > 6mg/L).

SCY-078

The oral formulation of SCY-078 will be administered in this study. The oral formulation allows for a combination strategy for the entire duration of the antifungal treatment. At the time of initiation of this study, an intravenous formulation of SCY-078 is not available. The dose selected for study SCY-078-206 took into consideration the data from the study in invasive candidiasis patients (SCY-078-202) as well as the PK data available from other Phase 1 studies with the oral formulation of SCY-078.

In summary:

Population Pharmacokinetic Modeling and Simulation

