10.3 Exploratory Endpoints

Efficacy as measured by:

- Absolute and percentage changes in serum β-D-glucan from Baseline at Weeks 1, 2, 4 and 6
- Percentage of subjects with the following changes in serum β-D-glucan from Baseline (if positive):
 - Fifty percent reduction or greater at Weeks 1, 2, 4 and 6
 - Twenty-five percent reduction or greater at Weeks 1, 2, 4 and 6
 - Any percent reduction at Weeks 1, 2, 4 and 6
 - o Negative serum β -D-glucan at Weeks 1, 2, 4 and 6

- Percentage of subjects that convert from positive plasma *Aspergillus* PCR at Baseline to negative at Weeks 1, 2, 4 and 6
- Absolute change in Karnofsky score (unit change = 10) from Baseline to Days 42 and 84
- Time to achieve a 10-point improvement in Karnofsky score from Baseline
- Percentage of subjects with a recurrence of the baseline fungal infection within 42 days (Week 6) after EoT
- Relationship between GMI decrease and ACM at Days 42 and 84
- Days of hospital stay, and days of ICU stay
- Percentage of subjects who are able to receive on schedule administration of the planned therapies for their underlying condition

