8.2.4. GMI Reduction

GMI is assessed at screening, Day 1, Day 3, Day 5, Day 7, Day 10, Day 14, then every 14 days during treatment, at EoT and at Follow-up.

GMI reduction at a visit will be calculated as the baseline result minus the result at the visit.

GM reduction will be summarized, by treatment, for the Intent-to-Treat Population at Week 1 (Day 7), Week 2 (Day 14), Week 4 (Day 28) and Week 6 (Day 42).

In addition, percentage reduction will also be summarized.

Note, assessment of GMI endpoints will be based on the central laboratory results. Local results will be listed only.

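### SAP 8.2.15 plots last available GMI decrease by vital status, so subjects who die are read earlier than most survivors, and a general fall in GMI can separate the boxes without any link to death

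*SAP*

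**What the plan says.** Protocol 10.3 lists an exploratory endpoint, "Relationship between GMI decrease and ACM at Days 42 and 84", and gives no method. SAP 8.2.15 supplies one, for ITT subjects with positive serum galactomannan at baseline. On grouping it says: "At Day 42, subjects will be categorized as dead or alive". For each of the two groups, "a boxplot will be presented showing their last available GMI decrease, up to and including Day 42". The only exclusion is: "Should a subject have no post baseline GMI data then they will not be included in the plot". The second horizon follows the same rule: "The above plot will be repeated for Day 84".

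Two further provisions fix what is read and when. SAP 8.2.4 defines the quantity on the absolute scale, "GMI reduction at a visit will be calculated as the baseline result minus the result at the visit", and adds percentage reduction as a further summary. It also gives the schedule: "GMI is assessed at screening, Day 1, Day 3, Day 5, Day 7, Day 10, Day 14, then every 14 days during treatment", then at EoT and follow-up. SAP 6.1 keeps repeat and unscheduled assessments out of data summaries. Neither document sets a landmark, a common reading day, a time-dependent model or a caveat for this comparison. The fixed-week GMI summaries in SAP 8.2.4 and 8.2.5 are by treatment arm, not by vital status.

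**The concern.** The grouping variable partly determines the reading day. A subject who dies before Day 42 cannot have a Day 42 GMI. A survivor still on treatment, which is recommended for at least 6 weeks, usually can. The decrease is not adjusted for elapsed time, so any average trend in GMI becomes a difference between the boxes.

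This matters because of how the results are meant to be used. Protocol 8.2 says "The information from this study is expected to guide the selection of clinically relevant endpoints" for a larger Phase 3 study and names serum galactomannan among the markers of interest. A display that tends to put the dead below the alive under ordinary GMI decline would lend GMI support as a mortality marker that the data may not contain.

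**Working it through.** The documents state no figure for this analysis, so there is nothing to reproduce. The check asks what the plot shows when GMI and death are generated independently.

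**Inputs from the documents.** GMI visits on Days 3, 5, 7, 10 and 14, then every 14 days on treatment (SAP 8.2.4). 22 subjects randomized (SAP 12). Six-week mortality in the combination-therapy trial cited in Protocol 8.1: 26/135 = 19.3% and 39/142 = 27.5%, pooled 65/277 = 23.5%.

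**Assumed, because the documents give no values.** Baseline GMI median 1.5 (log-SD 0.6, floor 0.5); exponential decline with half-life 7, 14 or 28 days; measurement log-SD 0.25; deaths uniform or front-loaded over 42 days; 30% dead by Day 84.

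**Step 1, by hand.** With baseline B and half-life h, the decrease at day t is B × (1 − 2^(−t/h)). For B = 1.5 and h = 14:
- Day 14: 1.5 × (1 − 0.5) = 0.75.
- Day 42: 1.5 × (1 − 0.125) = 1.31.

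The kinetics are identical and only the reading day differs.

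**Step 2, null simulation to Day 42** (400,000 subjects, 23.5% dead, uniform death times, absolute scale). The median last reading is Day 14 in the dead (Day 10 if deaths are front-loaded) and Day 42 in the alive. P is the probability that a randomly chosen survivor has a larger decrease than a randomly chosen subject who died; 0.50 means no association.

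| Half-life | Median decrease, dead | Median decrease, alive | P, uniform deaths | P, front-loaded deaths |
|---|---|---|---|---|
| 7 days | 1.05 | 1.44 | 0.64 | 0.71 |
| 14 days | 0.74 | 1.25 | 0.71 | 0.78 |
| 28 days | 0.45 | 0.92 | 0.73 | 0.79 |

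On the percent scale P is 0.83 to 0.87 with uniform deaths.

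**Step 3, how far the result moves** (Day 42, absolute scale, uniform deaths):
- 30% stop sampling early (half-life 14): 0.67.
- GMI levels off at half of baseline: 0.62.
- Very fast decline (half-life 3 days): 0.56.
- Flat GMI: 0.50.
- Rising GMI: 0.15, so the artefact reverses.

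**Step 4, Day 84.** The median last reading is Day 42 in the dead and Day 84 in the alive. P is 0.64 (half-life 14) and 0.70 (half-life 28). It is 0.60 at half-life 14 when many subjects stop sampling before Day 84.

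**Step 5, different kinetics.** Decay of median 0.07 per day (log-SD 0.5), 25% dying uniformly over Days 1 to 42, 15% assay noise. Median last-available percent decrease is 66% in the dead and 95% in the alive. With the same assumed baseline, the absolute medians are 0.90 and 1.36, with P about 0.68.

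**Step 6, trial size** (6,000 null trials of 22 subjects). The dead show the lower median in 76%, 87% and 90% of trials at half-lives 7, 14 and 28 days, against 50% expected. No test is planned; an illustrative 5% Wilcoxon test would reject in 15%, 28% and 34%. With only 15 subjects (half-life 14) the figures are 83% and 21%.

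**Step 7, landmark.** Reading everyone at Day 7 or Day 14, among those alive and sampled then, gives P of 0.497 to 0.502 in the Day 42 declining scenarios of Step 2. At half-life 14 the Day 7 medians are 0.41 in both groups. With 22 subjects and a Day 7 landmark, the dead have the lower median in 49% to 50% of trials and the illustrative test rejects in 4% to 5%. Under the Step 5 kinetics the medians are 40% and 40% at Day 7, and 63% and 63% at Day 14.

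**Step 8, cost of the landmark.** Expected deaths by Day 42: 22 × 0.235 = 5.2 (4.2 to 6.0 across the two cited arms). With deaths uniform over Days 1 to 42, the share before Day 7 is 6/41 = 15% and before Day 14 is 13/41 = 32%. That leaves about 4.4 and 3.5 deaths, and fewer once the plot is restricted to subjects positive at baseline.

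**The case against.** The strongest reply is about proportion. This is one exploratory boxplot with no planned test, to be evaluated as data allow, with about 5 expected deaths. Individual listings will let a reader see when each subject was last sampled, and a corrected plot on 4 or so deaths would also support little inference. All of that stands and limits the priority. It does not cure the bias, because few deaths make the boxes noisier without making the reading days comparable.

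Several stronger readings are tempting, and the documents do not support them.
- A reader might infer that the plot shows a link whatever GMI does. It needs GMI to fall on average. The reduction endpoints at Weeks 1, 2, 4 and 6 make decline the anticipated case, but no document gives a slope.
- A reader might take the percent-scale contrast as the size. SAP 8.2.4 defines reduction on the absolute scale first, where the effect is smaller.
- A reader might assume that every survivor contributes a Day 42 or Day 84 value. The survival contacts on those days schedule no GMI and may be by telephone. A survivor ending treatment at Day 56 has follow-up near Day 98, so the last reading before Day 84 is at Day 56. This narrows the gap; Steps 3 and 4 show that it remains.
- A reader might call this the only planned evidence on GMI and mortality. SAP 8.2.16 relates GMI to Global Response, which has death as a category, and Protocol 8.2 rests Phase 3 endpoint choice on the study as a whole.
- A reader might extend the defect to SAP 8.2.16 to 8.2.18. Those are headings without a method and state no last-available rule.

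**Conclusion.** The concern holds, conditionally. Subjects who die are read earlier than most survivors, so under an average decline in GMI the plot leans towards larger decreases in survivors when there is no relationship. With deaths spread evenly to Day 42, P on the absolute scale is about 0.56 to 0.73 instead of 0.50, and up to 0.79 with front-loaded deaths. These sizes depend on assumed kinetics and death times. The direction was the same in every declining scenario tested, while a flat GMI gives no artefact and a rising one reverses it. The primary safety endpoint and the DRC Global Response are not affected, so this is a modest, inexpensive correction.

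**What to change.** In SAP 8.2.15, make a landmark plot the main display. Among baseline-GMI-positive subjects alive with a GMI at Day 7, show the decrease from baseline to Day 7 by later vital status at Day 42 and at Day 84. Repeat this with a Day 14 landmark. Report the number of deaths before each landmark and the number alive but without a GMI at that visit.

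The last-available plot may stay as a supplementary display, since it keeps late values such as a rise before death. It should carry a footnote that reading days differ between the groups.

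Both visits are already scheduled, so no new data are needed. The cost is the early deaths left out, as counted in Step 8, from an already small total. This point requires no change to SAP 8.2.16 to 8.2.18.
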